5.2 Subject Dispositions

The number and percentage of subjects who were screened and enrolled or not enrolled, and the reasons for not enrolling, will be summarized for the Screened population. For the Enrolled population, the number and percentage of subjects who received SUBLOCADE, completed the study, discontinued and the reasons for discontinuing during the induction or the SUBLOCADE phase, will be summarized.

The number and percentage of subjects comprising each analysis population will be summarized.

The number and percentage of subjects failing entry criteria will be summarized overall and by individual criterion for the Screened population.

5.3 Key Endpoints Analysis

The analysis of key endpoints will be performed using the FAS, unless otherwise specified. The derived endpoints will be listed for the FAS.

The key timepoints for the analysis are defined as 1, 6, 12, 24, and 48 hours post-SUBLOCADE.

5.3.1 COWS Total Score Increase by ≥ 6 - Definition of Endpoint(s)

The total score on the COWS assessment at each timepoint will be calculated as the sum of the 11 individual item scores at the timepoint. Incomplete COWS assessments are not expected. (Note the term COWS will refer to COWS total score throughout this section.)

The endpoint is the cumulative event rate of an increase in COWS total score by ≥ 6 from the pre-SUBLOCADE value.

5.3.2 COWS Total Score Increase by ≥ 6 - Main Analytical Approach

The cumulative event rate for COWS Total Score increase by ≥ 6 from the pre-SUBLOCADE value will be estimated via the Kaplan-Meier method (1958), using the 5 key timepoints, 1, 6, 12, 24 and 48 hours after SUBLOCADE administration (i.e., time=0). Note that for the 1-hour key timepoint the event is referred to as precipitated withdrawal. A subject will be considered in the risk evaluation set at a specific key timepoint if the subject had a pre-SUBLOCADE COWS assessment and either 1) an increase in COWS by ≥ 6 from the pre-SUBLOCADE value within the current time interval (from the previous key timepoint to the current key timepoint), or 2) had a COWS assessment at the current key timepoint and all the prior key timepoints. If a subject has missing COWS assessment at one or more above key timepoints (1, 6, 12, 24 and 48 hours after SUBLOCADE administration), the subject is censored at the last key timepoint prior to the first missing timepoint.

The values for the event occurrence, time, and censoring parameters are assigned sequentially for the subject disposition events according to the order and criteria in Table 7.

Table 7 Parameters for Kaplan-Meier Method

Order of assignment	Disposition Event	Event of COWS Total Score Increase by ≥ 6	Time (hours)	Censored
1	An increase in COWS total score by ≥ 6 from the pre-SUBLOCADE value at any timepoint (scheduled or unscheduled) within 48 hours after SUBLOCADE injection	Yes	Nominal time of the first key timepoint on or after the COWS assessment meeting an increase in COWS total score by ≥ 6 from the pre-SUBLOCADE value	No
2	Missing COWS assessment at a key timepoint and without an increase in COWS total score by ≥ 6 from the pre-SUBLOCADE value within 48 hours	No	Nominal time of last key timepoint prior to the first missing key timepoint (i.e., 0, 1, 6, 12 or 24)	Yes
3	Completed COWS assessment at 1, 6, 12, 24, and 48 hours and without an increase in COWS total score by ≥ 6 from the pre-SUBLOCADE value within 48 hours	No	48	Yes

A Kaplan-Meier plot of the cumulative event rate from time=0 to 48 hours will be produced.

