14.3 Analysis Populations

14.3.1 Full Analysis Set (FAS)

The FAS population consists of all subjects who receive a SUBLOCADE injection and are evaluable for precipitated withdrawal; i.e., having data for at least 1 COWS assessment before SUBLOCADE injection and COWS assessments for 48 hours after SUBLOCADE injection. The FAS will serve as the primary population for the analysis of key endpoints in this study.

14.3.2 *Safety Analysis Set*

The safety population will be used for the safety analysis, and it consists all subjects who received at least 1 dose of SUBLOCADE. The safety population will serve as the primary population for the analysis of other safety assessments.

14.3.3 *TM Buprenorphine Analysis Set*

The TM Buprenorphine Analysis Set consists of all subjects who received at least 1 dose of TM buprenorphine. This analysis set will be used for analysis of the exploratory safety endpoint.

14.3.4 *PK Analysis Set*

The PK Analysis Set will be used for the Exploratory PK endpoint analysis and will consist of all subjects who receive the SUBLOCADE injection and are evaluable for PK, i.e., having an adequate number of PK samples collected to derive PK parameters. Subjects in the PK population with protocol deviations or events that impact the quality of the PK data will be assessed on a case-by-case basis.

14.4 **Analysis of Key and Exploratory Endpoints**

14.4.1 *Key Endpoints*

The number and percentage of subjects who experience precipitated withdrawal (defined as an increase in COWS by ≥ 6 from the pre-SUBLOCADE value) within approximately 1 hour after SUBLOCADE administration will be summarized. The frequency count, percentage and its 2-sided 95% exact confidence interval (CI) using binomial distribution (Clopper-Pearson method) will be constructed for precipitated withdrawal from the pre-SUBLOCADE value, using the FAS.

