The number and percentage of subjects with ≥ 6 -point increase in COWS within the first 6, 12, 24, or 48 hours post SUBLOCADE administration will be summarized using the FAS. As this is a cumulative endpoint, once a subject has a ≥ 6 -point increase in COWS, the subject will be counted for that timepoint and all subsequent timepoints. The denominator at each timepoint will be the number of subjects who have a pre-SUBLOCADE COWS assessment and either 1) have a ≥ 6 -point increase in COWS at or before the timepoint, or 2) have at least one post-SUBLOCADE COWS assessment within the timepoint interval. COWS assessments occurring at unscheduled visits will be included in the derivation.

The AUC will be calculated using the linear trapezoidal method, i.e.,

$$AUC = \frac{1}{2} \sum_{i=0}^n (T_{i+1} - T_i)(C_{i+1} - C_i)$$

where T_i is the i^{th} time value, C_i is the i^{th} COWS score, and n is the number of time values. Inherent to this formula, missing COWS scores are imputed in a linear manner.

The area under the curve (AUC) of COWS score from the time of administration of SUBLOCADE (i.e., time 0) through 6, 12, 24 and 48 hours after SUBLOCADE administration will be calculated using the FAS, and summarized using descriptive statistics for continuous endpoints (e.g., n, mean, median, SD, minimum and maximum).

The total score on the COWS and opioid craving visual analogue scale (OC-VAS) during the treatment period (i.e. at each assessment timepoint from administration of TM buprenorphine at Day 1 through EOT) will be summarized using descriptive statistics for continuous endpoints for the absolute value and change from the pre-TM Buprenorphine and pre-SUBLOCADE values. The analysis will use the FAS and observed data.

14.4.2 *Exploratory Endpoints*

The number and percentage of subjects who experience precipitated withdrawal from TM buprenorphine (defined as an increase in COWS by ≥ 6 from prior to the most recent dose of TM buprenorphine before SUBLOCADE administration) will be summarized using the TM Buprenorphine analysis set. The number, percentage and its 2-sided 95% exact CI using binomial distribution (Clopper-Pearson method) will be constructed using observed data.

Peak and overall plasma exposure to NMP following a single SC injection of 300 mg SUBLOCADE will be evaluated. The following PK parameters for NMP will be derived by non-compartmental analysis:

- C_{\max} : maximum observed plasma concentration

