5.3.5 Normalized AUC for COWS Total Score Post-SUBLOCADE Injection - Main analytical approach

The normalized AUC of COWS from the pre-SUBLOCADE value (i.e., time=0) through the key scheduled time points of 1, 6, 12, 24 and 48 hours (i.e., the analysis time intervals) after SUBLOCADE administration will be summarized using descriptive statistics for continuous endpoints.

A subject is included in a given analysis time interval if the subject has both the pre-SUBLOCADE COWS value (i.e., non-missing COWS at time=0) and the COWS assessment at the terminal scheduled timepoint for that analysis time interval or at a later timepoint up to 48 hours. Intermittent missing COWS total scores at a key timepoint other than 48 hours will be imputed via linear interpolation using the closest non-missing COWS total scores before and after the missing COWS total score. The two closest non-missing COWS total scores and their associated timepoints are defined as (C_b, T_b) and (C_a, T_a) where b=before and a=after. The imputed value for the missing COWS total score, for C_m , is

$$C_m = C_b + (T_m - T_b) \frac{C_a - C_b}{T_a - T_b}$$

where T_m is the imputed time as defined below.

Thus, the missing COWS total score at the terminal scheduled timepoint for the analysis interval will not be imputed if there is no observed COWS total score following that timepoint up to 48 hours, and subjects with such missing COWS total score will be excluded from the calculation for that analysis interval. All observed COWS total scores (at scheduled timepoints and unscheduled timepoints with a non-missing time) within the analysis interval of interest will be used. The actual time will be used for calculation. If the actual time for a scheduled assessment is missing, the time will be imputed for the AUC calculation as

$\text{Time}_{\text{current COWS}} = \text{actual time SUBLOCADE injection} + \text{nominal time}_{\text{current COWS}}$

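### SAP Table 7 censors event-free subjects, but not event subjects, at the first missed key COWS, so Kaplan-Meier rates after 1 h are too high if gaps are random and intermittent

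*SAP*

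**What the plan says.** SAP 5.3.2 estimates the cumulative rate of a COWS rise of 6 or more on five key timepoints (1, 6, 12, 24 and 48 h). Table 7 assigns each subject to the first row that fits.

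- Row 1 makes the subject an event if the rise occurs "at any timepoint (scheduled or unscheduled) within 48 hours after SUBLOCADE injection". Earlier missed key COWS play no part.
- Row 2 covers "Missing COWS assessment at a key timepoint and without an increase in COWS total score" in the 48 h. The censoring time is "Nominal time of last key timepoint prior to the first missing key timepoint". Later observed COWS do not alter it.
- Row 3 censors at 48 h a subject with all five key COWS and no event.

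The text above the table says that, if a key COWS is missing, "the subject is censored at the last key timepoint prior to the first missing timepoint". It makes no exception for events. Of 1 h, the SAP says: "Note that for the 1-hour key timepoint the event is referred to as precipitated withdrawal".

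Other parts of the plan treat gaps differently. For the AUC, SAP 5.3.5 says: "Intermittent missing COWS total scores at a key timepoint other than 48 hours will be imputed via linear interpolation". Under Protocol 14.4.1, the cumulative denominators kept an event-free subject if he or she did "have at least one post-SUBLOCADE COWS assessment within the timepoint interval", and the exact interval for the 1 h rate "will be constructed for precipitated withdrawal from the pre-SUBLOCADE value, using the FAS".

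SAP 6.2 explains that Kaplan-Meier became the main method because of the amount of missing COWS. SAP 1.1 gives possibly informative missingness as the reason for adding adjudication.

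**The concern.** Two subjects with the same record up to a missed COWS get different treatment according to what happens afterwards. The one who later has an event stays in every risk set up to that event. The one who stays event-free is removed from the gap onwards. This takes event-free subjects out of the denominators and leaves event subjects in, which pushes the later rates up.

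This is the main analysis of the first key endpoint, and the SAP's stated purpose is estimation (Section 2), so bias in the estimate matters in itself. No planned analysis isolates the error: 5.3.3.1 reuses the same rule within strata, and 5.3.3.2 replaces the event definition with clinical judgement.

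**Working it through.** **1. The plan's own figures.** SAP Section 3 gives the chance of at least one event with n = 15. 1 − 0.90^15 = 0.794 and 1 − 0.95^15 = 0.537, as printed. The plan has no figure for the effect of Table 7. I take n = 15 and the 10% rate from there. Missing rates, onset times and duration of a rise are my assumptions.

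**2. The rule on two subjects.** A and B each miss only the 1 h COWS. A rises at 24 h; B never rises.

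| | Table 7 row | Time | In risk sets at |
|---|---|---|---|
| A | 1 | 24, event | 1, 6, 12, 24 h |
| B | 2 | 0, censored | none |

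The text differs from the table for A. The censoring sentence would censor A at 0. The risk-set sentence would admit A only at 24 h, because A lacks the 1 h COWS at 1, 6 and 12 h.

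**3. Constructed example, n = 15.** Two events at 24 h, 13 event-free. With no gaps the estimate is 2/15 = 13.3%. If 2 of the 13 missed only the 1 h COWS it is 2/13 = 15.4%; if 6 did, 2/9 = 22.2%.

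**4. All onsets at 1 h.** True rate 10%, each COWS missing independently with probability m, rise visible at 1, 2 and 3 h:

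- 1 h rate: q = 0.1(1−m) / [0.1(1−m³) + 0.9(1−m)]
- 6 h hazard: h = 0.1m(1−m²) / [0.1m(1−m²) + 0.9(1−m)²]
- Rate from 6 h on: 1 − (1−q)(1−h)

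For m = 5/10/20%, q = 9.9/9.9/9.8% and h = 0.6/1.3/3.2%, so the rate is 10.5/11.1/12.7% and flat from 6 h. The 1 h rate is slightly low, not high. If the rise shows at the 1 h COWS only, h = 0 and q = 10.0% at every m: no error.

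**5. All onsets after 24 h.** If every event is detected, the 48 h rate is 0.1 / [0.1 + 0.9(1−m)^5] = 12.6/15.8/25.3%. Simulation, which allows undetected events, gives 12.3/15.3/23.8%.

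**6. Onsets spread evenly over the 13 scheduled COWS.** Simulation, 400,000 subjects per scenario, rise visible at up to 3 consecutive COWS:

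| | 6 h | 12 h | 24 h | 48 h |
|---|---|---|---|---|
| True | 3.8% | 5.4% | 7.7% | 10.0% |
| Table 7, 10% missing | 4.5% | 6.5% | 9.8% | 13.6% |
| Table 7, 20% missing | 5.3% | 8.0% | 13.0% | 19.4% |

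At 5% missing the 48 h value is 11.6%.

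**7. Other conditions (48 h, truth 10%).**

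- Even onset, rise visible at one COWS only, 5/10/20% missing: 11.1/12.4/16.1%.
- Even onset, same gaps confined to a quarter of subjects: 11.2/11.9/11.2%.
- Dropout with 6 to 33% lost by 48 h: 10.0 to 10.3%.
- Brief rises with 5% of key but 50% of other COWS missed: 8.3%, because undetected events outweigh the excess.
- COWS missed because of withdrawal (30/50/70% missed while elevated, 10% otherwise): 11.0–13.9 / 10.2–11.8 / 7.9–8.9%.

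**8. Two alternative rules.** *Last-observed*: an event-free subject is censored at the last key timepoint at or before the last COWS seen within 48 h. *Outcome-blind*: everyone is censored before the first missed key COWS, and an event counts only if its assigned key COWS and all earlier ones were observed.

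| 48 h estimate, truth 10% | Last-observed | Outcome-blind |
|---|---|---|
| Independent gaps, rise at up to 3 COWS | 9.9–11.3% | 10.0% |
| Rise at one COWS only | 8.0–10.0% | 8.7–10.0% |
| 50% missed while elevated | 8.0–8.7% | 5.8–6.4% |
| 70% missed while elevated | 5.7–6.6% | 3.6–4.2% |

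With all onsets at 1 h, the last-observed rule lowers the 1 h estimate to 9.5/9.0/8.0%. A plain count among subjects with a 1 h COWS gives 10.0% at all three missing rates.

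**The case against.** The strongest reply is that the SAP worries about informative gaps, and nothing in it says that gaps were random. If half of the COWS are missed while scores are high, Table 7 happens to land near the truth and both alternatives fall below it. In a safety study that is the worse direction. Under random gaps Table 7 errs upwards, which is conservative for a safety claim. This stands as a reason not to insist on a new main rule. It does not make Table 7 sound: its closeness to 10% there comes from two errors offsetting.

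Other points limit the weight of the concern:

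- Nothing is tested, and n = 15 is imprecise (exact interval for 2/15: 1.7 to 40.5%).
- SAP 5.3 lists derived endpoints by subject, so a crude count can be recovered.
- Out-of-window COWS keep their nominal visit (SAP 6.3), and the permitted sleep skips are at 16 and 20 h, which are not key timepoints. Both reduce key misses.
- SAP Section 3 allows extra enrolment for evaluability at the key timepoints. The n = 15 example does not model that. Extra enrolment would not remove the large-sample bias.
- The AUC is not an exact parallel. Interpolating a score is a weaker step than declaring a subject event-free across a gap.
- Row order settles the programming despite the conflicting sentences, and 5.3.2 sets out the rule openly. A reader might infer concealment from SAP 6.2, which does not mention the loss of event-free subjects; the documents do not support that.

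A reader might also infer that the 1 h precipitated-withdrawal rate is inflated. It is not: an event-free subject who misses 1 h leaves that denominator, but a 1 h rise not seen at 1 h also leaves the numerator.

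**Conclusion.** The rule is wrong as written: censoring depends on later outcome. Under random intermittent gaps it overstates the rates after 1 h. The excess grows to 48 h when onsets are spread or late, stays flat from 6 h when all onsets are at 1 h, and vanishes when a 1 h rise shows at one COWS only. With a true 48 h rate of 10%, even onset and 5/10/20% independent gaps, the estimate is about 11.6/13.6/19.4%.

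The mechanism is certain from the text; the size is not. The SAP says that COWS were missing but gives no rate or pattern, so the documents do not support a claim that the reported rates are inflated by any particular amount, or at all. Dropout gives almost no error, zero events give none, and the direction is unknown if withdrawal itself caused the gaps. The point should be fixed, but it does not undermine the study.

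**What to change.** 1. Bring the free-text censoring sentence and the risk-set sentence of SAP 5.3.2 into line with Table 7.
2. Add the outcome-blind and last-observed versions defined above as sensitivity analyses, reported beside the main Kaplan-Meier estimate and the adjudicated count.
3. Report the 1 h rate separately: events by 1 h over subjects assessed by then, with the protocol's Clopper-Pearson interval.
4. State that Table 7 overstates rates after 1 h under random gaps, and that both alternatives understate them if COWS are missed because of withdrawal.

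Making the last-observed rule the main analysis is optional, because it lowers the 1 h estimate and understates events under informative gaps.

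The cost is SAP wording and a little programming, with no new data. The outcome-blind version is less precise: at n = 15, even onset and 20% missing, its standard deviation is 12.2 points against 8.1 for the last-observed version.

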5.3.3 COWS Total Score Increase – Sensitivity Analyses

5.3.3.1 Stratification Variables

If sample size permits, the cumulative event rate analysis will be repeated for each of three stratification variables: number of TM BUP doses during induction phase (1 dose, ≥ 2 doses) and during SUBLOCADE treatment phase (0 dose, ≥ 1 dose), and by enrollment before or after re-training (see [Section 5.6](#)).

5.3.3.2 Event Adjudication

An event adjudication committee, consisting of members external to Indivior, will perform adjudication of the data. The committee will review data from enrolled subjects and based on their clinical judgement, assess for each subject:

- whether precipitated withdrawal occurred following TM BUP
- whether precipitated withdrawal occurred within 48 hours post-SUBLOCADE injection, and if so at what study timepoint it occurred

The details of the adjudication committee membership and process will be defined in a committee charter.

The frequency count, percentage and its 2-sided 95% exact confidence interval (CI) using binomial distribution Clopper-Pearson method (Clopper 1934) will be constructed for adjudicated precipitated withdrawal following TM BUP and adjudicated precipitated withdrawal within 48 hours post-SUBLOCADE injection. The analysis for adjudicated precipitated withdrawal post-SUBLOCADE injection will be performed cumulatively by timepoint if there are any adjudicated events.

5.3.4 Normalized AUC for COWS Total Score Post-SUBLOCADE Injection - Definition of endpoint

The area under the curve (AUC) for COWS total score from the pre-SUBLOCADE value to a later time point will be calculated using the linear trapezoidal method, i.e.,

$$AUC = \frac{1}{2} \sum_{i=0}^n (T_{i+1} - T_i)(C_{i+1} + C_i)$$

where T_0 is the time of the SUBLOCADE injection, C_0 is the COWS total score at the pre-SUBLOCADE timepoint, T_i is the i^{th} time value, C_i is the i^{th} COWS total score, and n is the number of time values. Inherent to this formula, intermittent missing COWS total scores are imputed in a linear manner.

For each analysis time interval (AUC_{0-1hr} , AUC_{0-6hrs} , $AUC_{0-12hrs}$, $AUC_{0-24hrs}$, $AUC_{0-48hrs}$) the AUC value will be normalized across subjects for the actual duration (in hours) of the time interval. The formula for normalized AUC for a given subject in a given analysis time interval is:

$AUC_{\text{normalized}} = AUC_{\text{calculated}}$ divided by the actual duration of time interval (hrs)

Note: the normalized AUC for COWS can be interpreted as the averaged AUC per hour or the averaged COWS over a time interval, as if the COWS was measured hourly during that time interval. For example, the AUC_{0-1hr} is the average of the COWS total scores assessed at time=0 and time=1 hour. AUC_{0-6hrs} is the average of the COWS total scores assessed from time=0 to time=6 hours, as if the COWS total score was assessed hourly.

5.3.5 Normalized AUC for COWS Total Score Post-SUBLOCADE Injection - Main analytical approach

The normalized AUC of COWS from the pre-SUBLOCADE value (i.e., time=0) through the key scheduled time points of 1, 6, 12, 24 and 48 hours (i.e., the analysis time intervals) after SUBLOCADE administration will be summarized using descriptive statistics for continuous endpoints.

A subject is included in a given analysis time interval if the subject has both the pre-SUBLOCADE COWS value (i.e., non-missing COWS at time=0) and the COWS assessment at the terminal scheduled timepoint for that analysis time interval or at a later timepoint up to 48 hours. Intermittent missing COWS total scores at a key timepoint other than 48 hours will be imputed via linear interpolation using the closest non-missing COWS total scores before and after the missing COWS total score. The two closest non-missing COWS total scores and their associated timepoints are defined as (C_b, T_b) and (C_a, T_a) where b=before and a=after. The imputed value for the missing COWS total score, for C_m , is

$$C_m = C_b + (T_m - T_b) \frac{C_a - C_b}{T_a - T_b}$$

where T_m is the imputed time as defined below.

Thus, the missing COWS total score at the terminal scheduled timepoint for the analysis interval will not be imputed if there is no observed COWS total score following that timepoint up to 48 hours, and subjects with such missing COWS total score will be excluded from the calculation for that analysis interval. All observed COWS total scores (at scheduled timepoints and unscheduled timepoints with a non-missing time) within the analysis interval of interest will be used. The actual time will be used for calculation. If the actual time for a scheduled assessment is missing, the time will be imputed for the AUC calculation as

$\text{Time}_{\text{current COWS}} = \text{actual time SUBLOCADE injection} + \text{nominal time}_{\text{current COWS}}$

